6.10.18 Wound Photograph

Photographs will be used for qualitative visual documentation of changes in wound size and therefore the rigor of image acquisition will not be as great as that for quantitative measures. Photographs should be taken with a standard digital camera or phone with a minimum of 8 megapixels and auto focus. To

promote consistency within and among investigational sites, photography guidelines are described below.

Study photography guidelines are as follows:

1. Place a white or blue towel, paper, or sheet under the foot to serve as the background for the photo
2. Place the white ruled sticker labelled with the subject ID, and date, on the skin as near the wound as possible without covering the wound.
3. No other identifying information should appear in the frame.
4. The camera should be set to focus and flash automatically.
5. Position the camera parallel to the wound and approximately 12 inches from the wound.
6. Photographs should be saved on a secure location at the center and should be emailed on a regular basis to the sponsor. Sponsor will receive the photographs at [contact].

6.10.19 Off-Loading Device: Fitting and Instruction

Subjects will be provided with offloading devices such as those listed below or similar:

- Ossur DH Offloading Walker®
- Ossur DH Offloading Post-Op Shoe

Subjects will be counseled on the importance of offloading for healing purposes. Investigators will instruct subjects to avoid weight-bearing on the study leg as much as possible and to use the prescribed off-loading device whenever ambulatory.

6.10.20 Nutritional Guidelines

Subjects will receive coaching on appropriate nutrition as well as foods that may impact wound healing consistent with the Cleveland Clinic's Nutritional Guidelines to Improve Wound Healing. As a nutritional reference, subjects will be given a copy of Cleveland Clinic's Nutritional Guidelines to Improve Wound Healing (see Appendix C) upon study enrollment.

7 STATISTICAL CONSIDERATIONS

As a prospective clinical outcome and survivorship study, there are no specific hypotheses to be tested. Data analysis may be conducted intermittently as needed or as requested by investigators without a power penalty and consist primarily of summary statistics and inferential statistics for changes in dependent measures over time.

Specific data analyses may include but are not limited to:

- **Demographics** and other pre-treatment characteristics will be summarized and characterized with appropriate descriptive statistics including error measures. Statistics may include mean, mode, median, range, inter-quartile range, minimum, maximum, frequency, cumulative frequency percentage and cumulative percentage. Results may be presented in a narrative and graphically.
- **Subject reported and dependent outcome measures** will be summarized and thoroughly characterized with the appropriate descriptive statistics including error measures. Statistics may include mean, mode, median, range, inter-quartile range, minimum, maximum, frequency, cumulative frequency percentage and cumulative percentage. Results may be presented in a narrative and graphically. Measures collected at multiple timepoints will also be analyzed using inferential statistics to assess changes over time, of special interest post-treatment changes from pre-treatment values. As appropriate a repeated measure ANOVA or Wilcoxon signed rank

test will be completed for each outcome measure. If a significant trend is identified, significance among time points may be further explored using the appropriate pair-wise comparisons. In all cases a p-value equal to or less than 0.05 will be considered significant. No corrections for multiple pair-wise comparisons will be made.

Missing data will be ignored in statistical calculations while using the appropriate n (sample size) for any given statistic or test.

Sample Size Justification: The precision of the estimate of the proportion of subjects who successfully close will be determined.

Assumptions:

- A minimum 50 subjects
- A 95% Confidence Interval of the estimate
- A 2-sided confidence interval
- Using exact Clopper-Pearson estimation

The Confidence Intervals (CI) at selected success rates are as follows:

- @ 25%; CI = 25.4% Boundaries 13.8%-39.3%
- @ 50%; CI = 28.9% Boundaries 35.5%-64.5%
- @ 75%; CI = 25.4% Boundaries 60.7%-86.2%

Thus, a sample size of 50 should allow for a reasonable estimate of treatment success at 12 weeks and for reasonable comparisons both to the literature and a history of not healing.

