Study Contact	M. [name]. Head of Clinical Affairs Miromatrix Medical Inc [name]	[contact] X-112 [contact] [contact]

Study Synopsis

Protocol Number	2016002
Title	Effectiveness of MIRODERM® Biologic Wound Matrix in the Treatment of Hard-to-Heal Diabetic Foot Ulcers
Short Title	MIRODERM H2H DFU
Sponsor	Miromatrix Medical Inc.
Name of Product	MIRODERM® Biological Wound Matrix Fenestrated MIRODERM® Biological Wound Matrix Fenestrated Plus
Device Description See IFU for complete details	MIRODERM Biological Wound Matrix MIRODERM is a non-crosslinked acellular wound matrix that is derived from porcine liver and is processed and stored in a phosphate buffered aqueous solution. MERODERM is available in a variety of sizes to be trimmed to meet the individual patient's needs and comes with or without fenestrations. MIRODERM is packaged in an inner sterile pouch and outer non-sterile pouch.
Intended Use See IFU for complete details	MIRODERM Biological Wound Matrix This device is intended for the management of wounds including: 
 • Partial and full thickness wounds • Pressure ulcers • Venous ulcers • Diabetic ulcers • Chronic vascular ulcers • Tunneled, undermined wounds • Drainage wounds • Surgical wounds (donor sites/grafts, post-Mohs' surgery, post-laser surgery, podiatric, wound dehiscence) • Trauma wounds (abrasions, lacerations, second-degree burns, and skin tears) 
The device is supplied sterile and is intended for one-time use

Background	Estimates are 8% of the United States population are diabetic and up to 25% of these will experience at least one diabetic foot ulcer in their lifetime. Treatment of diabetic foot ulcers can cost \$28,000 per episode. The presence of a diabetic foot ulcer increases chances of infection and future amputation. It is thus important to heal ulcers as expediently as possible. Ulcers refractory to treatment are of special concern and may prove responsive to treatment with MIRODERM Biologic Wound Matrix.
Study Center(s)	Up to 10 study centers will participate in this clinical trial.
Planned Sample Size	A minimum of 50 and not more than 65 subjects will be enrolled into this study.

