13 SUSPENSION OR TERMINATION OF THE STUDY

The study may be terminated at any time by the sponsor, with no further obligation to follow-up subjects. The study will be closed and the data will be archived according to the appropriate regulations.

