19 PUBLICATION POLICY

All data, results and any intellectual property derived from the data or results of the study are the property of the sponsor. The sponsor may use the data as they deem necessary, such as for submissions to governmental regulatory authorities, disclosure to other investigators and scientific communications. Sponsor and Study Principal Investigator will actively participate and engage investigators to actively participate in scientific communication production of aggregated study data at the sponsor's discretion and with sponsor review of the publication(s). The study sponsor will be responsible for determining

publication procedures and resolving authorship issues. Authorship may be determined by various measures, including contribution to the study design and enrollment rate.

The sponsor recognizes the right of the investigators to publish data and results derived from the participation of their center. However, prior to submitting for publication, presentation, using for instructional purposes, or otherwise disclosing results obtained from the study, the investigator(s) agree to allow the sponsor a period of at least 30 days to review the proposed publication or disclosure prior to its submission for publication or other disclosure. If the proposed publication/disclosure risks the sponsor's ability to patent any invention related to the study, the publication or disclosure will be modified or delayed for a sufficient time to allow the sponsor to seek patent protection of the invention. This statement does not preclude the sponsor from having any editorial rights over the content of a publication or disclosure; however sponsor editorial comments shall be given no more weight than any other participant of the publication process.

Investigators may also request aggregate data summaries across all or a subset of all centers. These requests will be fulfilled at the sponsor's discretion. If the written contract for study conduct includes publication provisions inconsistent with this statement, then that contract's publication provisions shall apply rather than this statement

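### Section 7 permits any number of unscheduled interim significance tests at p ≤ 0.05 as if they were free; if an interim p-value is reported as a finding or drives stopping, the type I error exceeds 5%

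*Combined protocol and SAP*

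**What the plan says.** Section 7 opens by disclaiming hypotheses: "As a prospective clinical outcome and survivorship study, there are no specific hypotheses to be tested". It then says: "Data analysis may be conducted intermittently as needed or as requested by investigators without a power penalty". The same sentence describes these analyses as ones that "consist primarily of summary statistics and inferential statistics for changes in dependent measures over time", so they are not limited to summaries.

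The bullet on outcome measures prescribes a repeated measures ANOVA or Wilcoxon signed rank test for each measure and adds: "In all cases a p-value equal to or less than 0.05 will be considered significant". It continues: "No corrections for multiple pair-wise comparisons will be made". The Synopsis (Statistical Analysis) names wound area and quality of life as the measures tested over time, and adds a Z-test of the closure proportion against zero.

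Neither place gives a number or schedule of looks, an adjusted threshold, or a statement that early results are descriptive.

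On the end of enrolment, the Synopsis says: "A minimum of 50 and not more than 65 subjects will be enrolled into this study". Section 6.2 adds a 6-month enrolment period. No rule fixes where in the 50 to 65 range enrolment ends. Section 13 says: "The study may be terminated at any time by the sponsor, with no further obligation to follow-up subjects". Section 19 says: "Investigators may also request aggregate data summaries across all or a subset of all centers", with release at the sponsor's discretion.

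**The concern.** Testing accumulating data repeatedly at an unchanged 5% level gives chance several opportunities to cross the threshold. That raises the probability of a false positive. Section 7 speaks only of power, which is a different quantity, and so gives the impression that interim testing costs nothing.

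The absence of a formal hypothesis does not remove the problem, because the same section prescribes significance tests and a threshold for calling results significant. The treatment is open-label and single-arm, closure is judged by the treating physician, and the final sample size is left open. Nothing in the text keeps interim results away from the decision to stop or to report.

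At stake is the meaning of a significant change in wound area or SF-36 score. Large reductions in wound area would probably survive any adjustment; modest SF-36 changes are more exposed.

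**Working it through.** **Inputs.** Threshold p ≤ 0.05 (Section 7), taken as two-sided because sidedness is not stated. Sample size 50 to 65 (Synopsis). Enrolment over 6 months, about 26 weeks (Section 6.2). Outcome known by 12 weeks (Section 4.2). The number of looks is not given, so a range is shown.

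**1. The plan's own figures.** The Clopper-Pearson limits are the 0.025 quantile of Beta(x, n − x + 1) and the 0.975 quantile of Beta(x + 1, n − x). With n = 50:

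- x = 12.5: 13.84% to 39.26%, width 25.42 points
- x = 25: 35.53% to 64.47%, width 28.95 points
- x = 37.5: 60.74% to 86.16%, width 25.42 points

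These agree with Section 7 apart from rounding (28.9 stated for the middle width). They do not depend on interim looks.

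**2. Error rate with repeated looks.** For K equally spaced looks with no true change, Z_k = S_k/√k, where S_k is the sum of k independent standard normal increments. The error rate is the probability that |Z_k| ≥ 1.96 at one or more looks. It was simulated with 2,000,000 runs, then with a paired t-test on 50 subjects (200,000 runs) as a stand-in for the before-after tests.

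| Looks | Normal, equally spaced | Paired t-test, 50 subjects |
|---|---|---|
| 1 | 5.0% | 5.0% |
| 2 | 8.3% | 8.4% (n = 25, 50) |
| 3 | 10.8% | 10.5% (n = 20, 35, 50); 10.8% (n = 17, 34, 50) |
| 4 | 12.6% | 12.8% (n = 13, 25, 38, 50) |
| 5 | 14.2% | 14.5% (n = 10, 20, 30, 40, 50) |
| 10 | 19.4% | not run |

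Each row is for one test on one measure. The uncorrected pair-wise comparisons are a separate source of error and are not included.

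**3. When this applies.** The table counts a false positive if any look is significant. If only the test on the full final sample is reported, and stopping did not depend on results, the first row applies (5.0%), whatever was examined earlier.

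**4. The primary closure proportion.** Suppose enrolment is stopped between n = 50 and n = 65 so as to favour the estimate. The largest upward bias any sequential rule can produce, with the true rate p known and every outcome available at once, comes from backward recursion:

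- V_65(x) = x/65
- V_n(x) = max{ x/n, p·V_(n+1)(x + 1) + (1 − p)·V_(n+1)(x) } for n = 64 down to 50
- bias = E[V_50(X)] − p, with X binomial(50, p)

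The result is +0.6, +0.7 and +0.6 percentage points at p = 25%, 50% and 75%. Outcomes are in fact delayed. With 50 to 65 subjects over 26 weeks, between 50 × 12/26 = 23 and 65 × 12/26 = 30 subjects are still within their 12 weeks at any time. Treating all of these as unknown lowers the bound to about +0.4 to +0.5 points. Some closures are known earlier, so a realistic bound lies between these figures. The interval widths are 25 to 29 points.

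**5. The Z-test against zero.** If the true closure rate were zero, no closure would occur at any look. Repeated looks therefore cannot inflate this test.

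**6. What an adjusted threshold would be.** To hold 5% overall for one test with equally spaced looks at a constant (Pocock) level, each look needs a two-sided p of about 0.029 (2 looks), 0.022 (3 looks) or 0.016 (5 looks).

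**The case against.** The strongest defence is that the study is observational, disclaims formal hypotheses, bases its sample size on interval precision and promises no overall error rate. No interim test is scheduled and there is no efficacy stopping rule. Section 18 places the sponsor's analysis and final report after study completion. The 0.05 sentence closes a bullet on ANOVA, Wilcoxon and pair-wise tests, so carrying it over to interim looks is an inference. Section 13 is a general termination clause not tied to results, and Section 19 concerns aggregate summaries, not p-values.

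Much of this stands, and it limits the point to a conditional one. It does not dispose of it: Section 7 expressly allows intermittent inferential analysis, gives no other threshold for it, and assures the reader that there is no cost.

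Two stronger readings are tempting, and the documents support neither:

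- A reader might infer that every published p-value will have the wrong error rate. That does not follow, for the reason in step 3 of the working.
- A reader might infer that the open sample size could raise the closure rate by about 2 points. A bias of that size comes from taking the largest proportion over n = 50 to 65 with hindsight. That means seeing all 65 outcomes and then discarding enrolled subjects, which nothing in the plan permits. Even then, two-sided exact coverage stays at or above 95.4%.

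**Conclusion.** The point holds in conditional form. Section 7 is wrong to present unscheduled interim tests at p ≤ 0.05 as cost-free. Where an interim p-value is reported as a finding or influences stopping, the error rate for one test with no true change is about 8% (2 looks), 10.5% (3 looks) or 14% (5 looks) instead of 5%. This rests on two-sided tests, roughly even spacing and an assumed number of looks.

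The exposure lies in the secondary tests of wound area and SF-36. The sample-size intervals reproduce, the primary Clopper-Pearson interval is essentially untouched, and outcome-driven choice of n could move the closure estimate by at most about 0.6 to 0.7 points. The text deserves correction, but the point does not undermine the primary result.

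**What to change.** Replace the Section 7 sentence on intermittent analysis with:

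> Analyses before the last subject's last visit are descriptive only, without p-values. P-values and the primary 95% Clopper-Pearson interval come from one final analysis. No outcome summary is used to decide when enrolment ends between 50 and 65.

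Align the Synopsis (Planned Sample Size) and Section 6.2 with the last sentence. If interim p-values are wanted, name the looks in advance and use an alpha-spending boundary.

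The sponsor gives up interim p-values. Descriptive summaries for investigators remain available, and no extra subjects or data are needed. Because the document combines protocol and SAP, and the enrolment wording changes too, this is a minor protocol amendment and not an SAP edit alone.

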
Study Design and Procedures
	
This is a multi-center post-market, single-arm, prospective follow-up study
 
Assessment and Roll-in Phase
 
Subjects will be recruited by the treating physicians, screened for eligibility, invited to participate in the study and provide informed consent. The subject's demographics, medical history, co-morbidities and wound characteristics will be documented and the subject will complete a SF-36 quality of life questionnaire. Subject will be instructed on proper nutrition.
 
Wound will undergo sharp debridement, be traced, photographed, and dressed per standard of care. Two tissue sections of at least 2mm will be retained for histological analysis. Subject will be fitted with and instructed on an offloading device. Subjects will return for MIRODERM treatment in two weeks.
 
Treatment Phase
 
On treatment day, wound will undergo sharp debridement, be traced, photographed and MIRODERM Biologic Wound Matrix will be applied. After treatment, subjects will be considered enrolled into the trial. Details of treatment will be documented.
 
Subject will present weekly for the next twelve weeks. The dressing will be changed and may undergo further MIRODERM treatment if indicated. The wound will be traced and photographed. Physician will document their assessment on whether the wound is 100% closed.
 
Subjects whose wound is completely closed at or prior to 12-weeks post-treatment, will be instructed to return 1-week following for a confirmation visit. Subjects whose wound is not assessed as closed by 12-weeks post-treatment, will have two tissue sections of at least 2mm collected, complete a quality of life assessment, and will then be discontinued per protocol.
 
Confirmation Phase
 
Subject will complete a quality of life assessment and have their wound area photographed. Physician will confirm the wound is still closed and the subject will be discontinued per protocol. If wound has reopened subject will return to the treatment phase.

Subject Participation
	
Subjects can be expected to reasonably participate in the study for a minimum of 9 weeks and a maximum of 15 weeks depending treatment course.

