4.2 Primary Endpoint

The primary endpoint will be the proportion of subjects who achieve wound closure by or at 12-weeks post treatment with MIRODERM.

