6 CLINICAL PROTOCOL

6.1 Study design

This is a multi-center post-market, single-arm, prospective follow-up study evaluating outcomes and efficacy of MIRODERM Biological Wound Matrix to treat hard-to-heal DFUs.

Assessment and Roll-in Phase

Patients who suffer from a persistent neuropathic DFU will be recruited from the investigators practice and network, screened for eligibility, invited to participate in the study and provide informed consent.

The subject's demographics, medical history, co-morbidities and wound characteristics will be documented and the subject will complete a SF-36 quality of life questionnaire. Subject will be instructed on proper nutrition.

The DFU will be treated by the investigator with sharp debridement, be traced, photographed, and dressed per standard of care; dressing will be changed daily by the subject. Two tissue sections of at least 2mm will be retained for histological analysis. Subject will be fitted with and instructed on an offloading device. Subjects will return for MIRODERM treatment in two weeks. At the discretion of the investigator, subjects may also be seen 1-week after initial visit; however, this interim visit is not required by the study and will not be documented.

Treatment Phase

On treatment day, subjects will have their wound debrided as necessary, photographed, assessed using the E-Z Graph Wound Assessment System and treated using MIRODERM. They will be asked to return weekly for dressing and wound assessment. After treatment with MIRODERM, subjects will be considered enrolled into the trial. Details of treatment will be documented.

Weekly, for up to 12 weeks, subjects will return, have their wound assessed for closure. As clinically appropriate, they may have their wound debrided and treated using MIRODERM. The wound will be photographed and assessed using the E-Z Graph Wound Assessment System and treatment details will be documented as applicable. The subject will receive a \$25 gift card for attending the follow-up visit.

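### Investigators may ask for running results with no end-of-study condition, which could add to the bias that an unmasked, site-judged single-arm endpoint already carries

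*Combined protocol and SAP*

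**What the plan says.** **Access to results.** Section 7 (Statistical Considerations) says: "Data analysis may be conducted intermittently as needed or as requested by investigators". It sets no limit on the number, timing, content or recipients of these analyses. Section 19 (Publication Policy) adds: "Investigators may also request aggregate data summaries across all or a subset of all centers". The sentence that follows leaves each such request to the sponsor's discretion. It gives no criteria and does not require the study to have ended.

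**Who controls the endpoint.** Section 6.1 describes the design: "This is a multi-center post-market, single-arm, prospective follow-up study". No masking is described. The treating physicians recruit and screen (synopsis; sections 6.1 and 6.5.1). On closure, the synopsis says: "Physician will document their assessment on whether the wound is 100% closed". A physician also confirms closure one week later (section 6.1, Confirmation Phase). No independent assessor is named.

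**The endpoint.** Section 4.2 reads: "The primary endpoint will be the proportion of subjects who achieve wound closure by or at 12-weeks post treatment with MIRODERM".

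**Safeguards in the plan.** Section 6.10.4 defines closure by full epithelial cover, absence of exudate and no remaining need for a dressing. Sections 6.1 and 6.8.1 return a reopened wound to follow-up. Photographs and original tracings go to the sponsor (sections 6.10.17 and 6.10.18), and monitors compare the database with source documents (section 8).

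**The concern.** An investigator who learns the running closure rate while subjects are still being recruited and assessed could be influenced in two ways: in which patients to invite next, and in how to call a wound that is nearly closed. The plan allows investigators to ask for that information and does not say when it may be given.

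The estimate is meant for comparison with the literature and with a history of not healing (end of section 7). With no concurrent control to absorb a shift in selection or in calls, any shift passes directly into the primary proportion.

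This differs from the type I error of repeated looks. Section 7 says that "there are no specific hypotheses to be tested", and the point would stand if no p-value were ever computed.

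**Working it through.** **1. The plan's own precision figures.** Inputs from section 7: n = 50 ("A minimum 50 subjects"), 95% two-sided Clopper-Pearson interval. Lower limit = Beta(0.025; x, n − x + 1); upper limit = Beta(0.975; x + 1, n − x); x = n × rate.

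| Rate | x | Computed limits | Computed width | Stated |
|---|---|---|---|---|
| 25% | 12.5 | 13.84% to 39.26% | 25.42 | 13.8% to 39.3%, 25.4 |
| 50% | 25 | 35.53% to 64.47% | 28.95 | 35.5% to 64.5%, 28.9 |
| 75% | 37.5 | 60.74% to 86.16% | 25.42 | 60.7% to 86.2%, 25.4 |

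The stated figures reproduce. They describe sampling error only, and restricting access to results would not change them.

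**2. Could results be known while recruitment is open?** Section 6.2 plans enrolment over 6 months, about 26 weeks. The endpoint is read by week 12. Assume even accrual, which the plan does not state. The first 12-week outcome then exists with 26 − 12 = 14 weeks of enrolment left, and 14/26 × 50 ≈ 27 of 50 subjects would be treated after it. Wounds that close early are known sooner. There is thus a period in which running results exist and both selection and closure calls are still to be made.

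**3. What would pooled results add to what a site already knows?** Each investigator sees their own subjects weekly. Section 6.2 caps a centre at 13 subjects. At n = 50, at least 50 − 13 = 37 outcomes come from other centres. That outside information, and any formal tally of a site's own results, is all that the access rule adds.

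**4. Scale of one changed call.** The synopsis gives the enrolment range: "A minimum of 50 and not more than 65 subjects will be enrolled into this study".
- n = 50: 1/50 = 2.0 points, against a half-width at 50% of 28.95/2 ≈ 14.5 points.
- n = 65: 1/65 ≈ 1.5 points, against a half-width at 50% of 25.33/2 ≈ 12.7 points (same method, x = 32.5).

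The documents give no error rate for closure calls and no way to link a changed call to knowledge of interim results. The calculation stops here.

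**5. How far do the safeguards reach?** The definition of closure narrows the room for judgement, but exudate and the need for a dressing are still judged at the site. Confirmation is also made by a site physician, and the endpoint wording in section 4.2 does not say that closure must be confirmed to count. Section 6.10.18 treats photographs as qualitative, and no section uses photographs or tracings to verify closure. Checking data against source documents would not detect a lenient call recorded the same way in both.

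**The case against.** The strongest objection concerns cause. The exposure to assessor bias comes from an unmasked single-arm study in which the treating physician judges closure, and it would exist if no analysis were ever run. That stands. Only the increment from seeing aggregate results belongs to this point, and withholding them leaves the same physician making the same calls.

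The evidence for mid-study release is also limited. Section 7 permits the request without saying that results go back to the person asking, although that is the natural reading. The summaries in section 19 sit among publication rules and depend on the sponsor's discretion. Section 18 places the final analysis, and the report to investigators, after completion. The case therefore rests mainly on one clause in section 7. That clause nevertheless allows analyses during the study, and no section withholds effectiveness results from sites.

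Two stronger readings are tempting:
- A reader might infer that access to running results would bias the closure proportion. The documents show an opportunity only. They do not show that results were or will be released, or which way any effect would run.
- A reader might add decisions on re-applying the matrix as a further source of assessor bias. Re-application when clinically indicated (section 6.7.3) is part of the treatment under study, so an effect of it on closure is not an error of assessment.

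Finally, a post-market study without a formal hypothesis may reasonably choose running descriptive summaries. That answers a concern about error rates but does not give sites a reason to see closure results early; no stated objective depends on it.

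**Conclusion.** The point holds in a limited form. Sections 7 and 19 let investigators ask for accumulating results with no end-of-study condition, and the same unmasked physicians select subjects and call and confirm closure. Access could add to an existing exposure to selection and assessor bias. The plan's safeguards reduce that exposure without removing it.

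The size of the added bias is unknown. The 2 points per call at n = 50 (about 1.5 at n = 65) is a unit of scale, not an estimate. A reader might multiply it by a guessed number of calls: three to five would give 6 to 10 points at n = 50. Nothing in the documents supports such a count or ties it to interim knowledge.

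The conclusion assumes that a requested analysis may reach the person who requested it, and that at least some requests could be met before follow-up ends. The text allows both and confirms neither. This is an inexpensive improvement to the plan and does not by itself invalidate the primary estimate.

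**What to change.** In sections 7 and 19, state that pooled or by-centre effectiveness results will not be released to investigators or site staff until the last subject has completed the final 12-week or confirmation visit and the data are locked. Exempt safety information explicitly.

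The change is to wording only. Sample size, visits, assessments and the stated intervals stay as they are. The cost is that investigators wait for aggregate results until the end of a study planned to last one year. The change removes one avoidable route to bias; the unmasked assessment of closure by the treating site remains and should be acknowledged as a limitation when the proportion is reported.
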